### **3.3 Sample Size**

This is a retrospective cohort study. Based on screening of the hospital's electronic medical records and application of the predefined inclusion and exclusion criteria, a total of 50 patients were included. Among them, 30 patients underwent conventional anastomosis and 20 patients underwent ileocecal valve reconstruction. All surgeries and follow-up were conducted in the Department of General Surgery, Second Affiliated Hospital of Army Medical University.

### **3.4 Study Factors and Observation Indicators**

Clinical data will be collected from patients undergoing laparoscopic right hemicolectomy in the Department of General Surgery, Second Affiliated Hospital of Army Medical University, starting from the date of ethics committee approval.

Observation Indicators:

#### **Surgical Safety and Feasibility:**

Successful completion of surgery without anastomotic leakage, anastomotic bleeding, or stenosis.

No severe perioperative complications.

#### **Intraoperative Indicators:**

Total operative time

Anastomosis time

Intraoperative blood loss

Intraoperative blood transfusion volume

Incision length

Proximal and distal resection margins

Total number of lymph nodes harvested

Number of positive lymph nodes

#### **Postoperative Indicators:**

Postoperative complications within 30 days

Postoperative inflammatory markers

Time to first flatus

Time to first bowel movement

Time to first ambulation

Time to formed stool

Length of hospital stay

Reoperation rate

Readmission rate

Mortality rate

Bristol Stool Form Scale (BSFS) score

Defecation frequency

Urgency frequency  
Incidence of fecal incontinence

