## 2. Objectives

This is a retrospective study that systematically collects data from patients who have undergone laparoscopic radical right hemicolectomy for colon cancer in our department. Patients are categorized into two groups based on the type of anastomosis: the conventional anastomosis group and the ileocecal valve function reconstruction group. This study aims to investigate the impact of ileocecal valve (ICV) function reconstruction on postoperative complications and bowel function recovery in patients following right hemicolectomy.

The outcomes of interest include anastomotic leakage, anastomotic bleeding, anastomotic stenosis, wound infection, time to first flatus, time to first defecation, time to stool formation, incidence of postoperative diarrhea, and Bristol Stool Form Scale classification.

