### **3.7 Data Management and Statistical Analysis**

Statistical analyses will be performed using SPSS version 22.0. Categorical variables will be expressed as n (%) and compared using the Chi-square ( $\chi^2$ ) test. Continuous variables will be tested for normality using the Shapiro-Wilk test (S-W test). Data conforming to normal distribution will be presented as mean  $\pm$  standard deviation ( $\bar{x} \pm s$ ), and comparisons between groups will be performed using the t-test. A P-value  $< 0.05$  will be considered statistically significant.

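### Section 3.7 gives the Bristol Stool Form Scale, an ordered outcome, no suitable test: chi-square ignores its order, and the t-test route usually closes with no replacement named

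*Protocol*

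**What the plan says.** Section 2 (Objectives) includes "Bristol Stool Form Scale classification" in its list of outcomes of interest. Section 3.4, under Postoperative Indicators, lists the "Bristol Stool Form Scale (BSFS) score". Neither section says how many levels the scale has or how it will be summarised.

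Section 3.7 sets the analysis rules. For one class of variable: "Categorical variables will be expressed as n (%) and compared using the Chi-square" test. Continuous variables are first checked by Shapiro-Wilk. Then "Data conforming to normal distribution will be presented as mean" and standard deviation, and "comparisons between groups will be performed using the t-test". The section names no rank, trend or ordinal method and no test for data that fail the normality check. It does not assign the Bristol scale to either class.

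Section 3.3 fixes the groups at 30 conventional and 20 reconstruction patients. Section 3.6 makes 30-day anastomotic complications the primary endpoint and three recovery times the secondary endpoints. The Bristol scale is not among them.

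**The concern.** Stool form runs in order from hard to loose. The benefit hypothesised for the reconstructed valve is a shift along that order, towards formed stool. The protocol's two labels for the scale lead to different places under section 3.7:

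- **As a classification**, it goes to chi-square. That test asks whether the groups differ in any way at all, on as many as six degrees of freedom if seven levels occur, and treats the levels as unordered names.
- **As a score**, it goes to the t-test, but only if normality holds. A short integer scale seldom passes Shapiro-Wilk at these sample sizes, and the section then stops.

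The analyst would either use a test poorly matched to the hypothesis or choose one after seeing the data. Because the 50 patients come from records already screened, sample size cannot make up for an inefficient test.

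**Working it through.** **No figure to reproduce.** The protocol states no power, effect size or stool-form distribution. The check therefore compares the tests under stated assumptions and over a range.

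**Inputs from the protocol.** Group sizes 30 and 20 (section 3.3); significance level 0.05 (section 3.7).

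**Assumptions.** Two-sided testing; seven levels; a proportional-odds shift, logit P(Y ≤ k | reconstruction) = logit P(Y ≤ k | conventional) + ln(OR), with OR from 2 to 6. Four base distributions were used:

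- uniform: 1/7 each
- loose: 1, 2, 7, 15, 20, 30, 25%
- bell: 4, 10, 20, 32, 20, 10, 4%
- three levels: about 20, 30, 50% on types 4, 5 and 6, with almost nothing elsewhere

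**Step 1: power.** 4,000 simulated datasets per scenario, so the Monte Carlo standard error is at most √(0.5 × 0.5 / 4000) = 0.008. Chi-square is the Pearson test on all observed levels. The ratio is chi-square power divided by Mann-Whitney power.

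| Base | OR | Chi-square | Mann-Whitney | Ratio | t-test |
|---|---|---|---|---|---|
| Uniform | 2 | 0.110 | 0.262 | 42% | 0.264 |
| Uniform | 3 | 0.249 | 0.548 | 45% | 0.554 |
| Uniform | 4 | 0.401 | 0.757 | 53% | 0.752 |
| Uniform | 6 | 0.640 | 0.923 | 69% | 0.913 |
| Loose | 2 | 0.126 | 0.259 | 49% | 0.263 |
| Loose | 3 | 0.273 | 0.541 | 50% | 0.541 |
| Loose | 4 | 0.435 | 0.748 | 58% | 0.754 |
| Loose | 6 | 0.689 | 0.921 | 75% | 0.922 |
| Bell | 2 | 0.089 | 0.249 | 36% | 0.256 |
| Bell | 3 | 0.227 | 0.550 | 41% | 0.550 |
| Bell | 4 | 0.391 | 0.741 | 53% | 0.740 |
| Bell | 6 | 0.637 | 0.926 | 69% | 0.926 |
| Three levels | 2 | 0.212 | 0.249 | 85% | 0.262 |
| Three levels | 3 | 0.418 | 0.503 | 83% | 0.522 |
| Three levels | 4 | 0.619 | 0.708 | 87% | 0.722 |
| Three levels | 6 | 0.841 | 0.901 | 93% | 0.905 |

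With no shift (OR 1) the rejection rates were 0.035-0.053 for chi-square, 0.046-0.048 for Mann-Whitney and 0.049-0.050 for the t-test.

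**Step 2: analytic cross-check.** Take a 1-df test with 80% power. Its noncentrality is (1.960 + 0.842)² = 7.85. Spreading the same noncentrality over more degrees of freedom gives power 0.709 on 2 df (three levels) and 0.521 on 6 df (seven levels). The pattern agrees with step 1: the loss grows with the number of occupied levels.

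**Step 3: the t-test route.** Shapiro-Wilk at 0.05, applied to each group separately, no shift between groups, 3,000 datasets:

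| Base | Rejects, n = 30 | Rejects, n = 20 | Rejects in either group |
|---|---|---|---|
| Bell | 55% | 36% | 70% |
| Uniform | 88% | 56% | 95% |
| Loose | 99% | 84% | over 99% |

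So even a symmetric, bell-shaped scale would usually leave the t-test route.

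**The case against.** **The t-test is not at fault for power.** A reader might infer that both tests in section 3.7 ignore the ordering and lose about half the power. That is wrong for the t-test: it uses the order through equally spaced scores, and its power was within about 0.02 of Mann-Whitney in every scenario. The weakness on that route is only that it usually closes and nothing follows.

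**The size of the loss is not a property of this plan.** A reader might also take a loss of about half as a fixed figure. The protocol gives no stool-form distribution, no effect size and not even the number of levels. The loss is about half or more only for small to moderate effects with most levels in use. This objection stands, which is why a range is reported.

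**Sparse cells.** Twenty patients over seven levels average 20/7 = 2.9 per cell, which might suggest an invalid chi-square. The simulated error rate did not exceed 0.053, so false positives are not the problem; power is.

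**Importance.** The scale is one of 14 postoperative indicators and stands outside the endpoint hierarchy. The documents do not support calling it the key measure of benefit. This also stands. The rank test is no cure either: at odds ratio 3 its power is only about 0.55.

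**A separate analysis plan may settle it.** One may exist and could name an ordinal method. But section 3.7 states a general rule for categorical data, and such a plan would have to depart from it. The lack of a fallback after a failed normality check is general to section 3.7 and also bears on the secondary recovery times; this point concerns only the Bristol scale.

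**Conclusion.** The point holds in a limited, conditional form. Section 3.7 leaves the Bristol scale unclassified, and neither of its rules serves an ordered outcome. If the scale is treated as categorical, chi-square keeps about 36-50% of rank-test power at odds ratios of 2-3, 53-58% at 4 and 69-75% at 6 when seven levels are occupied, but 83-93% over odds ratios 2 to 6 when only three are. If it is treated as continuous, almost no power would be lost, but normality would be rejected in about 70% to over 99% of samples, with no test then named.

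These figures rest on assumed distributions, a proportional-odds shift, two-sided testing at 0.05 and the stated 30 and 20 patients. The consequence is small because the scale is neither a primary nor a secondary endpoint. It is a worthwhile refinement, not a threat to the study's main conclusions.

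**What to change.** Add one sentence to section 3.7: *BSFS type is ordinal and will be compared between groups by the Wilcoxon rank-sum (Mann-Whitney) test, with a proportional-odds ratio and 95% CI; chi-square is kept for nominal variables.* Use the same description of the scale in sections 2 and 3.4, so that it is not a classification in one place and a score in the other.

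The cost is that sentence and the matching label. The analysis uses the stool-form values the protocol already plans to extract and asks for no further variables. It does not depend on a normality check, so the choice of test no longer turns on the observed data.

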### **3.2 Study Setting and Population**

This is a single-center observational study. All clinical data are derived from patients who have previously undergone laparoscopic radical right hemicolectomy in the Department of General Surgery.

Patients will be grouped according to the type of anastomosis (exposure factor):

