**Metabolic parameters:**

blood glucose, lipid profile, glycated hemoglobin (HbA1c), and other physiological indicators

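### Stool form, defecation frequency, urgency and incontinence are compared only as postoperative levels between non-randomised groups, so a preoperative difference in bowel habit can pass as an effect of the anastomosis

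*Protocol*

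**What the plan says.** Protocol section 2 sets the aim as the impact of valve reconstruction "on postoperative complications and bowel function recovery in patients following right hemicolectomy", and it names the Bristol classification and postoperative diarrhea among the outcomes of interest.

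Section 3.4 lists what is observed. Its sub-headings cover surgical safety, intraoperative, postoperative, follow-up and metabolic items; none is preoperative. The Bristol score, "Defecation frequency", urgency frequency and fecal incontinence all stand under the postoperative sub-heading, without an assessment time. The metabolic items, "blood glucose, lipid profile, glycated hemoglobin (HbA1c), and other physiological indicators", stand under their own sub-heading, with no indication of when they are measured.

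The study is a retrospective cohort grouped by the anastomosis performed (sections 3.1 and 3.2). Section 3.3 gives the sizes: "30 patients underwent conventional anastomosis and 20 patients underwent ileocecal valve reconstruction".

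Section 3.7 gives two between-group comparisons. For categorical data: "Categorical variables will be expressed as n (%) and compared using the Chi-square" test. For normally distributed continuous data: "comparisons between groups will be performed using the t-test". Significance is declared below 0.05. No adjustment for any patient characteristic is mentioned.

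Section 3.6 names three secondary endpoints: the times to first flatus, first bowel movement and formed stool. The four bowel-habit items and the metabolic values are not endpoints there.

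**The concern.** A patient who had loose or frequent stools, urgency or incontinence before surgery is counted exactly like one who developed them afterwards. Randomisation would make the two groups alike before surgery on average, with only chance differences left. Here group membership follows the operation received, so nothing in the design balances prior bowel habit.

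If the groups differed before surgery, part of that difference carries through to the postoperative level, and the unadjusted test credits it to the anastomosis. The bias can run either way: it can create an apparent benefit of reconstruction or hide a real one.

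The gap begins in the data list. A later analysis plan can add a covariate, but not one that was never extracted.

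**Working it through.** **Plan's own figure.** The only figure to reproduce is the total: 30 + 20 = 50, which agrees. The protocol gives no effect size, SD or power, so nothing further can be checked against it.

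**Inputs from the protocol.** n = 30 and 20 (section 3.3); unadjusted t-test at 0.05 (section 3.7). Sidedness is not stated; two-sided is assumed.

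**Inputs assumed, because the protocol gives none.** A systematic preoperative gap D of 0.3, 0.5 or 0.8 SD, and a pre/post correlation ρ of 0.3, 0.5 or 0.7. The anastomosis is taken to have no true effect.

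**Step 1. Standard error of the group difference, in SD units.** √(1/30 + 1/20) = √0.0833 = 0.289.

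**Step 2. Postoperative difference carried over from baseline.** d = D × ρ. For D = 0.5 and ρ = 0.5, d = 0.25 SD.

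**Step 3. Chance of p < 0.05 with no true effect.** Noncentral t with 48 degrees of freedom and noncentrality d / 0.289. For d = 0.25 the noncentrality is 0.866 and the rejection rate is 13.6%.

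| D (SD) | ρ = 0.3 | ρ = 0.5 | ρ = 0.7 |
|---|---|---|---|
| 0.3 | d = 0.09, 6.1% | d = 0.15, 8.0% | d = 0.21, 11.0% |
| 0.5 | d = 0.15, 8.0% | d = 0.25, 13.6% | d = 0.35, 22.1% |
| 0.8 | d = 0.24, 12.9% | d = 0.40, 27.4% | d = 0.56, 47.7% |

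Adjusting for the preoperative value brings the rate back to about 5% if the recorded value carries the whole difference. A crudely recorded baseline would remove only part of it.

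**Step 4. Precision, continuous items only.** ANCOVA multiplies the residual variance by 1 − ρ²: 0.91, 0.75 and 0.51 for ρ = 0.3, 0.5 and 0.7, a cut of 9%, 25% and 49%. A simple change score gives 2(1 − ρ): 1.4, 1.0 and 0.6. It loses precision when ρ is below 0.5, which favours ANCOVA over subtracting the baseline.

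**The case against.** **Recovery is measured.** A reader might infer that the study does not measure bowel recovery at all. The protocol does not support that. The three secondary endpoints in section 3.6 run forward from surgery and need no preoperative level to be defined. Prior stool form could plausibly bear on the time to formed stool, but that is ordinary confounding, not a missing reference point.

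**Metabolic values are undated.** A reader might also infer that glucose, lipids and HbA1c are compared as postoperative levels only. The protocol does not say so; it gives no time point. What stands is that the timing is unstated.

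**Chance imbalance is already covered.** The 0.289 SD is the ordinary standard error of a 30 versus 20 comparison, and the t-test allows for it. Only a systematic gap inflates the false-positive rate, and nothing in the protocol shows that one exists. Eligibility also narrows the room for it: other gastrointestinal disease is excluded apart from benign conditions, as is autoimmune disease such as Crohn's. This limits the concern, but ordinary variation in bowel habit remains.

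**Section 3.4 may not be a full variable list.** It also omits age and ASA score, which eligibility requires, so preoperative bowel data might be collected without being listed. This is fair. Still, no section names such an item, and the stated tests would not use it.

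**Models belong in an analysis plan.** The choice of model can often be left there. The value it would need cannot.

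**The records may be thin.** Section 3.5 says only that data come from the EMR; it does not show that prior stool form or urgency was recorded. This stands and shapes the fix.

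**Conclusion.** The point holds for four items: stool form, defecation frequency, urgency and incontinence. As planned, a group difference in any of them cannot be separated from a preoperative difference. For a continuous item the false-positive rate would be 13.6% in place of 5% at a gap of 0.5 SD and a correlation of 0.5, and 6.1% to 47.7% over the assumed range. Both inputs are assumptions. Neither these rates nor the precision gain transfers directly to an ordinal stool score or a yes/no incontinence outcome, although the direction of the problem is the same.

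The weight is moderate. None of the four is a section 3.6 endpoint, although section 2 names the Bristol classification among the outcomes of interest. For the metabolic values the concern is conditional on postoperative values alone being taken. Nor does the protocol say who chose the anastomosis or why, so the argument rests on the absence of randomisation and not on any particular selection by surgeons.

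**What to change.** - **Section 3.4:** add the preoperative value of the four bowel items, and preoperative glucose, lipids and HbA1c, extracted from the EMR where recorded. State when each bowel and metabolic item is assessed.
- **Section 3.7:** compare each item adjusted for the patient's own preoperative value, by ANCOVA for continuous items and by an ordinal or logistic model otherwise. Report new-onset urgency and incontinence.
- **Sections 3.2.1 and 3.2.2:** inclusion criterion 5 and exclusion criterion 4 require complete data. State that a missing preoperative value of these items does not exclude a patient; otherwise the added fields could shrink the 50. Report the number missing by group.
- **Fallback:** if an item's baseline is largely unrecorded, label that item descriptive and draw no conclusion about the anastomosis from it.

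The cost is some extra extraction from existing records for 50 patients. The downside is incomplete baseline data, probably more so for stool form, urgency and incontinence than for laboratory values.

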**Follow-up Indicators:**

Anastomotic healing status  
Gastrointestinal contrast imaging (e.g., iodine-based contrast, upper GI barium meal)  
Colonoscopy findings

**Metabolic parameters:**

blood glucose, lipid profile, glycated hemoglobin (HbA1c), and other physiological indicators

### **3.5 Data Collection Method**

All clinical data are obtained from the hospital's electronic medical record (EMR) system. A dedicated research coordinator is responsible for data extraction and verification.

### **3.6 Study Endpoints**

**Primary Endpoint:**

Postoperative complications within 30 days, specifically anastomotic leakage, anastomotic bleeding, and anastomotic stenosis.

**Secondary Endpoints:**

Time to first flatus  
Time to first bowel movement  
Time to formed stool

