## **4.3 Financial Burden to Participants**

All patients included in this study have completed surgery and were discharged prior to study initiation. This study involves retrospective data analysis only and will impose no additional financial burden on participants.

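### Time to formed stool has no rule for patients discharged before the event, so its t-test comparison can depend on length of stay

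*Protocol*

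**What the plan says.** Section 3.6 of the protocol names "Time to formed stool" as a secondary endpoint, beside the times to first flatus and first bowel movement. It gives no start point, observation window or rule for a patient in whom the event was not seen.

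On the source, section 3.5 states: "All clinical data are obtained from the hospital's electronic medical record (EMR) system". Section 4.3 adds: "All patients included in this study have completed surgery and were discharged prior to study initiation". No diary, telephone call or questionnaire is described. Section 3.4 lists "Length of hospital stay" among the postoperative indicators but gives no value. Its follow-up indicators cover healing, contrast imaging, colonoscopy and metabolic parameters, and do not include stool form.

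On the analysis, section 3.7 applies a Shapiro-Wilk test and continues: "Data conforming to normal distribution will be presented as mean" with standard deviation, and "comparisons between groups will be performed using the t-test". No time-to-event method is named, and nothing is said about data that fail the normality test.

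On missing data, inclusion criterion 5 (section 3.2.1) requires complete data, and exclusion criterion 4 (section 3.2.2) removes patients whose data are incomplete. Section 3.3 gives the cohort: "30 patients underwent conventional anastomosis and 20 patients underwent ileocecal valve reconstruction".

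**The concern.** Of the three secondary endpoints, formed stool is the one most likely to fall after discharge. The protocol's own background says that losing the valve can lead to bacterial overgrowth with diarrhea, and that the team's RISE rats formed stool earlier. Late stool formation is therefore what the authors expect more often in the conventional group.

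A patient sent home with loose stool, with nothing recorded afterwards, has no event time. Under the stated rules that patient either contributes nothing to the mean or, if criterion 4 is applied to this variable, is not in the cohort at all. Both are selection on the outcome, with two consequences:

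- **Shrinkage.** The slowest patients are lost, and more of them from the slower group, so a true benefit of RISE is understated.
- **Creation.** If one group goes home sooner, only its quicker times are seen. It then shows a shorter mean even when the groups do not differ.

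This endpoint carries part of the secondary objective on bowel recovery.

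**Working it through.** The protocol states no effect size, standard deviation, power or length of stay, so there is no figure of its own to reproduce beyond 30 + 20 = 50. Everything below except the group sizes and the 0.05 level is an assumption made to show direction and range. In both models nothing is recorded after discharge, and stool time *T* and length of stay *D* are independent. An event is observed if *T* ≤ *D*.

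**Check 1: log-normal times, closed form.** Log SD of *T* is 0.6 and of *D* is 0.25, so √(0.6² + 0.25²) = 0.65. With Φ the standard normal distribution function:

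- Share observed = Φ(ln(median *D* / median *T*) / 0.65)
- True mean = median *T* × exp(0.6²/2) = median *T* × 1.197
- Mean among observed = true mean × Φ([ln(median *D* / median *T*) − 0.36] / 0.65) / share observed

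Take median *T* as 12 days (conventional) and 8 days (RISE), with a median stay of 8 days in both.

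- Conventional: share Φ(−0.405/0.65) = 0.27; true mean 14.4; observed mean 14.37 × Φ(−1.178) / 0.266 = 6.4 days.
- RISE: share Φ(0) = 0.50; true mean 9.6; observed mean 9.58 × Φ(−0.554) / 0.50 = 5.6 days.
- The true difference of 4.8 days appears as 0.9, a loss of 3.9/4.8 = 81%.

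Other stays under the same model:

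| Median stay, both groups | Observed, conventional / RISE | True difference | Difference among observed |
|---|---|---|---|
| 8 days | 27% / 50% | 4.8 | 0.9 |
| 14 days | 59% / 81% | 4.8 | 1.7 |
| 20 days | 78% / 92% | 4.8 | 2.5 |

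With no true difference (median 10 days in both) and median stays of 7 and 9 days, the observed means are 5.5 and 6.5 days. That is a spurious 1.0 day in favor of the group discharged sooner.

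**Check 2: normal times, simulated at the actual group sizes.** This model suits a t-test better and has no long tail. *T* has SD 3 days and *D* has SD 2 days; n = 30 and 20; two-sided alpha 0.05 (the protocol does not state sidedness); 2,000 runs per scenario.

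True difference of 3 days (means 10 and 7), equal stays:

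| Mean stay | Observed, conventional / RISE | Difference among observed | Power, t-test on observed | Power, log-rank with censoring |
|---|---|---|---|---|
| 8 | 29% / 61% | 1.6 | 0.33 | 0.80 |
| 10 | 50% / 80% | 1.9 | 0.54 | 0.86 |
| 14 | 87% / 97% | 2.5 | 0.85 | 0.88 |
| 20 | nearly all | 3.0 | 0.92 | 0.89 |

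With fully observed data, the t-test has power of about 0.92 to 0.93.

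No true difference (mean 9 in both):

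| Mean stay, conventional / RISE | Spurious difference | Type I error, t-test on observed | Type I error, discharge day entered as the time | Type I error, log-rank |
|---|---|---|---|---|
| 9 / 9 | 0.0 | 0.04 | 0.05 | 0.05 |
| 10 / 8 | 0.9 | 0.14 | 0.34 | 0.046 |
| 11 / 8 | 1.25 | 0.23 | 0.53 | 0.048 |
| 16 / 14 | 0.24 | 0.06 | 0.05 | 0.06 |

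Both directions of bias appear under both models. Under the normal model both fade as stays lengthen; under the log-normal model the shrinkage fades more slowly because of the long tail.

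**The case against.** **The bias is not shown to be present.** This stands. The protocol gives no length of stay and no share discharged before stool formed. A reader might infer that patients discharged early certainly have no event time and that the comparison is certainly distorted. The documents do not support that. If nearly all stools formed in hospital, the t-test does little harm, as the 20-day row of the normal model shows.

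**Observation need not end at discharge.** This stands in part. The record system is not limited to the inpatient chart, section 3.3 places follow-up in the same department, and readmission and 30-day complications need later records. But the listed follow-up indicators omit stool form, and a date first noted at a clinic visit reflects when the visit took place.

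**A plain mean is not prescribed for all data.** This is true: the mean and t-test apply to data that pass the normality test. For other data the protocol states nothing, so no stated branch handles an event that was not reached.

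**Such details belong in a statistical analysis plan.** A plan not shown here could add a censoring rule, and its absence from the protocol alone would be no finding. But the protocol itself fixes the data source, the complete-data rule and the test. Following them as written selects on the outcome whenever some patients leave before stool forms.

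**Kaplan-Meier alone would not cure it.** This stands. Patients already removed under criterion 4 cannot be censored, so the eligibility wording has to change too. Censoring at discharge also assumes that discharge is unrelated to bowel recovery, and the simulations build in that independence.

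**Conclusion.** The concern holds conditionally. The protocol treats an event that can occur after discharge as a fully observed continuous variable, and its complete-data criteria may remove patients who lack a date. If a material share left hospital before stool formed and it was not recorded later, the group difference depends on length of stay.

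The size cannot be taken from the documents. Under the assumed inputs, equal stays of about 8 days hide 1.4 of 3.0 days (47%) in the normal model and 3.9 of 4.8 days (81%) in the log-normal model. A two-day difference in stay creates about 0.9 to 1.0 day where none exists. With long stays the effect becomes negligible in the normal model. These figures assume no recording after discharge and independence of stay and stool time.

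This is a secondary endpoint. A reader might infer that the primary complication endpoint is compromised as well. That would follow only if criterion 4 had removed patients from the cohort for want of a stool date, which the documents do not say. The change should be made, but the point does not undermine the study as a whole.

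**What to change.** 1. **Sections 3.2.1 (criterion 5) and 3.2.2 (criterion 4):** state that lack of a formed-stool date is not a reason for exclusion. Check whether any patient was excluded on that ground and, if so, restore them.
2. **Section 3.6:** define the endpoint as days from surgery to the first recorded formed stool, censored at the last record that documents stool form (discharge, or a later visit if stool form was noted there).
3. **Section 3.7:** for this endpoint, replace the t-test with Kaplan-Meier curves and a log-rank test, and report the number censored in each group. Do not average only the patients with a date, and do not enter the discharge day as the event time.
4. **Sensitivity analysis:** because discharge may depend on bowel recovery, add the proportion with formed stool by a fixed day that precedes most discharges. Choose the day without knowledge of group results, and count patients discharged earlier with unformed stool as not formed.

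**Cost.** The methods are standard and use stool dates and lengths of stay that the protocol already plans to collect. Restoring excluded patients would need further record extraction. A mean in days may no longer be reportable, and censoring at discharge may be informative.

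The fixed-day analysis will be thin. In the log-normal null scenario with stays of 7 and 9 days, about 12% to 19% have formed stool by day 5 or 6, roughly 2 to 4 of 20 and 4 to 6 of 30. A later day brings the length-of-stay bias back: by day 7 the proportions are 23% and 27% with no true difference. It is therefore a check and not a replacement for the main analysis.
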